For our Secondary Aim #4, we will use MMRM analysis to compare changes in six-minute walk distance, physical activity, and SF-36 PF and WIQ distance and speed scores at 26-week follow-up between the high-intensity exercise and control groups.

For our Secondary Aim #5, we will use MMRM analysis to compare changes in six-minute walk distance, maximum treadmill walking time, physical activity, and SF-36 PF and WIQ distance and speed scores at 52 week follow up between high intensity exercise and control groups.

For our Secondary Aim #6, we will use two sample two-tailed t-tests to compare changes in COX, citrate synthase, and mitochondrial DNA at 52-week follow-up between the low intensity vs. the high-intensity exercise group and between the low-intensity exercise and control groups. We will also compare change in nitrotyrosine muscle measurements between the high-intensity exercise and the control groups. We will repeat these comparisons for the participants who adhere to their prescribed exercise intensity, measured by the ActiGraph.

For our Exploratory Aim #1, we will use two sample two-tailed test compare patients' perception to exercise at 52-week follow-up between high and low-intensity groups. For our Exploratory Aim #2, we will evaluate the effect of modified combo intervention (weight loss + LITE home-based exercise) on six-minute walk distance at approximately 12 week follow-up. This pilot study was completed in 2018.

The significance level for the Primary Aim will be 0.05/2 to adjust for two comparisons between low-intensity and high-intensity arms and between low-intensity and control arms.

The significance level will be 0.05 for all secondary aims. Furthermore, Secondary Aims #4 and #5 were pre-specified but added after the LITE Trial was underway in response to two negative trials of home-based exercise in patients with PAD demonstrating that a high-intensity walking exercise program did not improve six-minute walk or other outcomes in people with PAD (5, 6).

PROTOCOL TITLE: Low InTensity Exercise intervention in PAD: The LITE Trial

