Power estimates. For all primary and secondary aims, we anticipate a 15% drop-out rate at 52-week follow-up, based on 12-month follow-up rates in our GOALS and SILC trials (52,55). We will randomize 305 participants. Of these, 120 will be randomized to the low-intensity intervention, 120 will be randomized to the high-intensity exercise intervention, and 65 will be randomized to the control group. We will enroll more participants in each exercise group than the attention control group because we anticipate that the effect size of the low vs. high intensity exercise comparison will be lower than the effect size of the low intensity vs. the control group. For our Primary Specific Aim, we will have 80% power to detect a minimum difference of 0.43 standard deviations (SD) between the low intensity vs. high intensity exercise groups and a difference of 0.52 SD between the low-intensity and the attention control groups, in change of six-minute walk distance at 52-week follow-up, using two-sided two-sample t-tests **with a significance of 0.025 to adjust for the two comparisons.** Low intensity exercise will be considered effective if either comparison (i.e. with high intensity exercise or with the attention control group) is statistically significant. The SD of the change in six-minute walk in our GOALS and SILC trials was approximately 60 meters. Therefore, our sample size allows us to detect a difference in change in six-minute walk of 26 meters and 31 meters, respectively, between the low vs. high intensity groups and between the low intensity and control groups. Prior studies have defined clinically meaningful changes in the six-minute walk as 30 meters (small meaningful change) and 50 meters (large meaningful change) (102,103). Thus, our power should be adequate to detect a clinically meaningful difference. For our Secondary Aim #1, we will have 80% power to detect a difference of 0.39 SD between the high vs. low intensity exercise interventions and a difference of 0.47 SD between the low-intensity intervention vs. control group, respectively, in changes of six-minute walk, physical activity, WIQ scores, and SF-36 scores at 26 –week follow-up using two-sided two-sample t-tests with a significance of 0.05. For our Secondary Aim #2, we will have 80% power to detect a difference of 0.39 SD between the high vs. low intensity exercise interventions and a difference of 0.47 SD between the low-intensity intervention vs. control group, respectively, in changes of maximal treadmill walking time, physical activity, and WIQ and SF-36 scores at 52-week follow-up, using two-sided two-sample t-tests with a significance level of 0.05. In our SILC trial, the observed differences between the intervention and control groups are 0.61 SD, 0.59 SD and 0.61 SD in changes of maximal treadmill walking time, WIQ distance, and SF-36 physical functioning scores, respectively (52). In a study by Gardner et al of supervised exercise in participants with PAD (73), the observed improvement in physical activity

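### Optional improvement, not an error: a Holm step-down for the two primary contrasts would add power at the same 5% family-wise error as the fixed 0.025 levels

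*Combined protocol and SAP*

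**What the plan says.** Section 11.1 (Data analysis plan) sets the level: "The significance level for the Primary Aim will be 0.05/2 to adjust for two comparisons". The two contrasts are low v high intensity and low intensity v control. Section 11.2 (Power analysis) repeats a "significance of 0.025 to adjust for the two comparisons" and bases the sample size on it, "using two-sided two-sample t-tests". For low v high the stated result is that "we will have 80% power to detect a minimum difference of 0.43 standard deviations (SD) between the low intensity vs. high intensity exercise groups". For the second contrast the corresponding figure is "a difference of 0.52 SD between the low-intensity and the attention control groups". With an SD of about 60 m these become 26 m and 31 m. Neither section gives an order of testing, a step-down, or a rule for passing on unused alpha, so the procedure is plain Bonferroni.

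Two further statements bear on the point. The Primary Aim in Section 1.2 asks about low intensity against high intensity and against attention control as separate questions. Section 11.2 then defines success: "Low intensity exercise will be considered effective if either comparison (i.e. with high intensity exercise or with the attention control group) is statistically significant".

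**The concern.** With a fixed 0.025 for each contrast, the second contrast is held to 0.025 even after the first has been declared significant. Nothing in the control of the family-wise error requires that. Once one null hypothesis has been rejected at 0.025, only one is left to protect, and it can be tested at the full 0.05.

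What is at stake is the second answer. Whether low intensity exercise works at all and whether it beats pain-inducing exercise are different questions. Section 11.2 expects low v high to be the smaller effect and enlarges both exercise arms for that reason. If low v control is significant, Holm would test low v high at 0.05. At that level Section 11.2's own 80%-power difference for this pair of arms is 0.39 SD (given for the secondary aims), against 0.43 SD at 0.025.

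**Working it through.** **Inputs (Section 11.2).** Randomised 120/120/65; 15% drop-out; two-sided 0.025 per contrast; detectable differences 0.43 SD and 0.52 SD; SD of change 60 m.

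**Evaluable numbers.** 120 × 0.85 = 102 in each exercise arm; 65 × 0.85 = 55.25 controls.

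**Standard errors in SD units.**
- Low v high: √(1/102 + 1/102) = 0.1400 (8.40 m).
- Low v control: √(1/102 + 1/55.25) = 0.1670 (10.02 m).

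**Reproducing the plan's figures.** The detectable difference at 80% power is (2.241 + 0.842) × SE.
- Low v high: 3.083 × 0.1400 = 0.432 SD (0.434 with the t distribution). The plan states 0.43.
- Low v control: 3.083 × 0.1670 = 0.515 SD (0.519 with t). The plan states 0.52.
- In metres: 0.43 × 60 = 25.8 and 0.52 × 60 = 31.2. The plan states 26 and 31.

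The plan's power figures therefore hold at 0.025.

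**Correlation of the two test statistics.** They share the low-intensity arm: (1/102) / (0.1400 × 0.1670) = 0.419.

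**Rules compared.** Write Z1 and Z2 for the two statistics.
- Bonferroni rejects a contrast when |Z| > 2.241.
- Holm rejects contrast 1 when |Z1| > 2.241, or when |Z1| > 1.960 and |Z2| > 2.241. The rule for contrast 2 is symmetrical.

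Every Bonferroni rejection is also a Holm rejection. Every extra Holm rejection is a second rejection, so the event that at least one contrast is significant is identical under the two rules.

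**Results.** Several million simulated pairs of normal statistics with correlation 0.419. Each cell is Bonferroni → Holm, in percent.

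| True effects (low v high, low v control) | Low v high | Low v control | Both | At least one |
|---|---|---|---|---|
| 0.43 SD, 0.52 SD | 79.7 → 84.6 | 80.8 → 85.4 | 68.2 → 77.6 | 92.3 → 92.3 |
| 26 m, 31 m | 80.3 → 85.0 | 80.3 → 85.0 | 68.3 → 77.7 | 92.4 → 92.4 |
| 26 m, 40 m | 80.3 → 86.7 | 96.0 → 97.0 | 78.4 → 85.8 | 97.9 → 97.9 |
| 30 m, 30 m | 90.8 → 93.0 | 77.4 → 83.9 | 72.8 → 81.4 | 95.4 → 95.4 |
| 50 m, 50 m | >99.9 → >99.9 | 99.7 → 99.9 | 99.7 → 99.9 | >99.9 → >99.9 |

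The 40 m value is an assumption that shows a larger effect against control; it is not a planning value in the documents. The 30 m and 50 m rows use the small and large meaningful changes quoted in Section 11.2.

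**Hand check of one row (26 m, 31 m).** Low v high under Bonferroni: 26/8.40 = 3.095, and Φ(3.095 − 2.241) = 80.3%. At least one: 80.3 + 80.3 − 68.3 = 92.3, which agrees with 92.4 up to rounding.

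**Error rates.**
- Both nulls true: the family-wise error is about 4.7% under either rule.
- One null true and the other effect very large: the error on the null contrast is 2.5% under Bonferroni and 5.0% under Holm.
- Low v high null and low v control at 31 m: 2.5% against 4.3%.

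Holm stays within 5% throughout.

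**The case against.** The strongest reply is that nothing here is wrong. Two tests at 0.025 hold the family-wise error at 5%, Sections 11.1 and 11.2 agree with each other, and the trial was sized at the stricter level, so each contrast already has its stated 80% power. That stands. A reader might infer that the plan is underpowered or that its multiplicity control is faulty; the reproduced figures support neither.

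A reader might also infer that fixed 0.025 levels lower the trial's chance of success. Under the either-comparison rule in Section 11.2 they do not: that chance is about 92% with both procedures, because Holm's first step is the Bonferroni test. The plan nowhere requires both contrasts to be significant, so the rise from 68% to 78% concerns a second claim and not the success criterion. That second claim still has value, because Section 1.2 asks about both comparators.

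Three further objections hold in part:
- The gain needs both effects to be real and moderate. It is largest near the minimum detectable differences and vanishes near 50 m.
- Bonferroni gives 97.5% intervals that always match its tests. Under Holm they may not. This is a real convenience, but it does not offset the power when the second contrast matters.
- Section 9.1 of this version describes trial results, including the direction of the intensity comparison. Relaxing a primary threshold at that stage would be post hoc. This limits when the change can be made; it does not alter the statistical comparison.

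**Conclusion.** The fixed 0.025 levels are valid and deliver what the plan states. Holm is a cheap improvement. At the plan's minimum detectable differences it adds about 5 percentage points of power per contrast and about 9 for both together, within the same 5% family-wise limit. It adds nothing to the probability of meeting the stated success rule, and almost nothing when both effects are near 50 m.

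The power figures assume true effects at the design values, a common SD of 60 m, 15% drop-out in each arm, a normal approximation, and completers only; any precision gained by the mixed model from 26-week data or baseline adjustment is ignored. Holm's control of the family-wise error rests on none of these, beyond each test being valid at its own level. The point is sound as design advice before unblinding, and not as a reason to re-test the primary contrasts now.

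**What to change.** Before unblinding, replace the fixed 0.05/2 level in Section 11.1 with a rule such as: *The two primary contrasts will be tested by the Holm procedure. The smaller p-value is compared with 0.025. If it is not significant, testing stops. If it is significant, the other p-value is compared with 0.05.* The rule works on p-values, so it applies equally to the mixed model and to the rank-sum fallback. Leave the power statement in Section 11.2 at 0.025, where it becomes conservative for each contrast, and report 97.5% intervals as simultaneous intervals.

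The cost is one sentence, with no change to sample size. Section 11.1 records that the primary method was changed on 8/27/2020 before any data were analysed, so an edit of this kind was feasible then. Two downsides should be stated in the SAP: a contrast significant only at the second step may have a 97.5% interval that includes zero, and the error rate on a single null contrast can rise from 2.5% to as much as 5% when the other effect is real.

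For this version, which already describes results, keep 0.025 as the formal rule and label any Holm result post hoc.

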11.0 Data and Specimen Management

11.1 Data analysis plan.

- A. **Data management.** We will use data management methods in place for our ongoing NHBLI-funded PAD studies. Data from baseline and follow-up study visits are acquired on paper forms and processed using the Teleform system by Cardiff Software. We have successfully used this system for over 8,000 patient visits in our previous and ongoing studies. Data are backed-up on multiple hard drives and copied to CDROM for secure off-site storage.
- B. **Data Safety Monitoring Board (DSMB).** We have identified nationally recognized experts to serve on the DSMB.

Statistical Analyses. Analyses will be performed according to the intention to treat principle. Data will be analyzed according to each participant's originally assigned group, irrespective of whether the participant adheres to his/her assignment. Prior to analyses, the distributions of the variables (changes) will be examined and necessary transformations will be performed. The balance of socio-demographic factors and prognostic factors (such as age, sex, race, ABI, comorbidities, and relevant medication use) will be compared between the three groups using ANOVA or chi-square tests. If there is any indication of major imbalance, proper analysis of covariance adjustments will be performed in data analyses.

NOTE: The original plan to use two sample two-tailed t-tests was changed to a mixed model for repeated measures analysis on 8/27/2020 prior to analyzing any data. This change was made because as of 8/27/202, investigators are projecting an approximately 16% loss to follow-up rate at 52 week follow-up. The mixed model for repeated measures will be used to adjust for missing data.

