
PROTOCOL TITLE: Low InTensity Exercise intervention in PAD: The LITE Trial

level as measured by accelerometer in the exercise group was more than 0.86 SD greater than that for the control group. Thus we should have adequate power to detect similar effect sizes. For our Secondary Aim #3, we will compare rates of ActiGraph-measured adherence to the prescribed exercise intervention (five exercise sessions per week for 45 minutes of walking exercise per session) between the low vs. high intensity exercise groups. Adherence will be defined as achieving at least 80% of the prescribed exercise intervention (see section C18). Based on the home-based component of our SILC trial, we expect the adherence rate in the high intensity exercise group will be about 30%. Our sample size provides 80% power to detect a minimum difference of 19% in the proportion of adherence between the low intensity and high intensity groups, based on the two-sided Z test with pooled variance using normal approximation for binomial distribution with a significance level of 0.05. For our Secondary Aims #4 and #5, we will have 80% power to detect a difference of 0.52 SD between the high-intensity intervention vs. control groups, in changes of six-minute walk distance, physical activity, and WIQ and SF-36 scores at 26-week and at 52-week follow-up, and in change of maximal treadmill walking time at 52-week follow-up, using two-sided two-sample t-tests with a **significance level of 0.05**. Therefore, we have adequate power for detecting differences similar to those observed in SILC trial. For our Secondary Aim #6, we will randomly select 50 participants from each of the three study groups. We will have 80% power to detect a difference of 0.61 SD between the low vs. high intensity exercise interventions, between the low-intensity exercise intervention and the control group, and between the high-intensity exercise intervention group vs. control group, respectively, in changes of citrate synthase, COX, and mitochondrial DNA at 52-week follow-up, using two-sided two-sample t-tests with a significance level of 0.05. In a randomized trial, Timmers et al reported observed differences in citrate synthase, COX, and mitochondrial DNA of 3.17 SD, 2.12 SD, and 0.75 SD, respectively, between a treatment and control group (104). Thus we should have adequate power.

11.3 Steps to secure data to maintain confidentiality during storage, use, and transmission.

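### The detectable difference of 0.52 SD given for Secondary Aims 4 and 5 does not match its stated alpha of 0.05; for those arm sizes it is 0.47 SD

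*Combined protocol and SAP*

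**What the plan says.** Section 11.2 (Power analysis) randomizes 120 participants to low intensity, 120 to high intensity and 65 to attention control. It applies a 15% drop-out rate to all primary and secondary aims. Three of its statements concern an exercise arm against control, all at 80% power with two-sided two-sample t-tests:

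- **Primary Aim, low intensity versus control, alpha 0.025:** "a difference of 0.52 SD between the low-intensity and the attention control groups".
- **Secondary Aims 1 and 2, low intensity versus control, alpha 0.05:** "a difference of 0.47 SD between the low-intensity intervention vs. control group".
- **Secondary Aims 4 and 5, high intensity versus control:** "we will have 80% power to detect a difference of 0.52 SD between the high-intensity intervention vs. control groups". The alpha for these aims is given at the end of the same sentence as a "significance level of 0.05".

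Section 11.1 (Data analysis plan) agrees on alpha: "The significance level will be 0.05 for all secondary aims". The paragraph on Aims 4 and 5 concludes: "Therefore, we have adequate power for detecting differences similar to those observed in SILC trial".

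**The concern.** The two exercise arms are the same size, so high intensity versus control and low intensity versus control have the same planned numbers. With the same test, power and alpha they must have the same detectable difference, yet one is given as 0.47 SD and the other as 0.52 SD. The second figure coincides with the Primary Aim figure, which was calculated at the stricter alpha of 0.025.

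What is at stake is how the high-intensity versus control result is read. A reader who accepts 0.52 SD will think the comparison less sensitive than the plan's own assumptions make it. For six-minute walk the two figures fall on either side of the 30 m that Section 11.2 cites as a small meaningful change. The mismatch also leaves a reader unsure which alpha the added aims were powered at, although the text on alpha is consistent.

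**Working it through.** **Inputs (Section 11.2 unless stated)**

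- Evaluable per exercise arm: 120 × 0.85 = 102.
- Evaluable controls: 65 × 0.85 = 55.25, taken as 55.
- Power 80%; two-sided two-sample t-test.
- Alpha 0.05 for Aims 4 and 5 (Sections 11.1 and 11.2); alpha 0.025 for the Primary Aim.
- SD of change in six-minute walk: 60 m.

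**Formula**

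Normal approximation: detectable difference in SD units = (z for 1 − alpha/2 + z for 0.80) × √(1/n1 + 1/n2). The noncentral t version was also solved and is given alongside.

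- Exercise versus control: √(1/102 + 1/55) = 0.1673.
- Low versus high intensity: √(1/102 + 1/102) = 0.1400.
- Sum of z values: 1.960 + 0.842 = 2.802 at alpha 0.05; 2.241 + 0.842 = 3.083 at alpha 0.025.

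**Step 1: reproduce the plan's other figures**

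| Comparison | Alpha | Normal | Noncentral t | Plan |
|---|---|---|---|---|
| Low v high, Primary Aim | 0.025 | 0.432 | 0.434 | 0.43 |
| Low v control, Primary Aim | 0.025 | 0.516 | 0.520 | 0.52 |
| Low v high, Aims 1 and 2 | 0.05 | 0.392 | 0.394 | 0.39 |
| Low v control, Aims 1 and 2 | 0.05 | 0.469 | 0.472 | 0.47 |

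The method is therefore the plan's own. The Aim 3 figure also reproduces: 30% against a higher rate, 102 per arm and a pooled Z test give 19.1 percentage points (plan: 19%). For Aim 6, 50 per arm less 15% leaves 42.5. Taking 42.5 to 43 evaluable gives 0.615 to 0.611 SD (plan: 0.61).

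**Step 2: Aims 4 and 5**

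- Alpha 0.05: 2.802 × 0.1673 = 0.469 (noncentral t 0.472), so **0.47 SD**. The plan says 0.52.
- Alpha 0.025: 3.083 × 0.1673 = 0.516 (noncentral t 0.520), so 0.52 SD.
- Power at 0.52 SD with alpha 0.05: 87% (noncentral t), not 80%.

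**Step 3: could another assumption give 0.52 SD at alpha 0.05?**

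- Using 55.25 or 56 controls: 0.47.
- No drop-out: 0.43.
- The 16% loss projected in Section 11.1 (100.8 v 54.6): 0.474, still 0.47.
- 25% drop-out: 0.50.
- One-sided alpha 0.05: 0.42.
- 85% power: 0.50. 90% power: 0.54.
- Drop-out of about 30% would be needed to reach 0.52, and the power analysis assumes 15%.

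**Step 4: consequence**

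- Six-minute walk: 0.47 × 60 = 28 m; 0.52 × 60 = 31 m.
- Power at alpha 0.05 for the differences cited from the SILC trial: 94% at 0.59 SD and 95% at 0.61 SD.

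**The case against.** The strongest defence is that the statement is loose rather than false. If 80% is read as at least 80%, it is true, because power at 0.52 SD is 87%. The plan writes of a minimum difference for the Primary Aim and Aim 3 but not for Aims 4 and 5. This does not hold up: the statements for Aims 1 and 2 also omit the word, and their figures are exact detectable differences.

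A second point is that the documents show a mismatch between number and alpha but not how it arose. The figure may have been computed at 0.025 and the alpha text settled separately, or simply carried over from the Primary Aim. Either history is inference. Because Sections 11.1 and 11.2 both state 0.05, the number is the part to correct.

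Three limits on importance do stand:

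- The aims were added in March 2020 with the trial under way, and nothing shows that 0.52 SD drove a design choice.
- The 0.47 SD is a t-test figure with a 52-week drop-out rate, whereas these aims will be analysed by mixed model for repeated measures and include 26-week outcomes. Correcting it makes the section consistent; it does not give the exact sensitivity of the planned analysis.
- The agreement for Aim 6 depends on rounding: 42 evaluable per arm would give 0.62. The contradiction does not rest on Aim 6, since Aims 1 and 2 alone show it.

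**Conclusion.** The concern holds. At the stated alpha of 0.05, 80% power and 15% drop-out, the detectable difference for high intensity versus control is 0.47 SD, not 0.52 SD. This rests on the plan's own arm sizes, drop-out rate and t-test, which reproduce its other figures for these arms.

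The error is 0.05 SD, about 3 m in six-minute walk at an SD of 60 m, and it is conservative. Severity is minor: the conclusion of adequate power for differences of the size seen in SILC stands under either figure.

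**What to change.** In Section 11.2, in the sentence on Secondary Aims 4 and 5, replace 0.52 SD with 0.47 SD. Keep the significance level at 0.05, as both Sections 11.1 and 11.2 state, and have the trial statistician confirm that 0.05 was the level intended.

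The cost is one number in the text. Nothing changes for participants, sample size, analysis or decision rule.
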